## **6.2 Product Complaint**

### **6.2.1 Definition**

A Product Complaint is any Complaint (see Section 6.0 for the definition) related to the biologic or drug component of the product or to the medical device component(s).

For a product this may include, but is not limited to, damaged/broken product or packaging, product appearance whose color/markings do not match the labeling, labeling discrepancies/inadequacies in the labeling/instructions (example: printing illegible), missing components/product, device not working properly, or packaging issues.

For medical devices, a product complaint also includes all deaths of a patient using the device, any illness, injury, or adverse event in the proximity of the device, an adverse event that could be a result of using the device, any event needing medical or surgical intervention including hospitalization while using the device and use errors.

Any information available to help in the determination of causality by the device to the events outlined directly above should be captured.

### **6.2.2 Reporting**

Product Complaints concerning the investigational product and/or device must be reported to the Sponsor within 24 hours of the study site's knowledge of the event via the Product Complaint form into the RAVE® electronic data capture (EDC) system or via the back-up paper form if EDC is unavailable. Product Complaints occurring during the study will be followed-up to a satisfactory conclusion. All follow-up information is to be reported to the Sponsor (or an authorized representative) and documented in source as required by the Sponsor. Product Complaints associated with adverse events will be reported in the study summary. All other complaints will be monitored on an ongoing basis.

Product Complaints may require return of the product with the alleged complaint condition (pen, etc.). In instances where a return is requested, every effort should be made by the investigator to return the product within 30 days. If returns cannot be accommodated within 30 days, the site will need to provide justification and an estimated date of return.

The description of the complaint is important for AbbVie in order to enable AbbVie to investigate and determine if any corrective actions are required.

## **7.0 Protocol Deviations**

AbbVie does not allow intentional/prospective deviations from the protocol unless when necessary to eliminate an immediate hazard to study subjects. The Principal Investigator is responsible for complying with all protocol requirements, and applicable local laws regarding protocol deviations. If a protocol deviation occurs (or is identified) after a subject has been enrolled, the Principal Investigator is responsible for notifying Independent Ethics Committee (IEC)/Independent Review Board (IRB) regulatory authorities (as applicable), and their assigned Clinical Monitor or the following AbbVie Clinical Monitor(s):

**Primary Contact:****Alternate Contact:**

Such contact must be made as soon as possible to permit a review by AbbVie to determine the impact of the deviation on the subject and/or the study.

For the purposes of this protocol, reportable deviations are defined as:

- Subject entered into the study even though she/he did not satisfy entry criteria
- Subject who developed withdrawal criteria during the study and was not withdrawn
- Subject who received wrong treatment or incorrect dose
- Subject who received excluded or prohibited concomitant treatment

**8.0                    Statistical Methods and Determination of Sample Size****8.1                    Statistical and Analytical Plans**

The primary objective of the statistical analyses is to determine the proportion of subjects with Ps who have a satisfactory response to ADA + MTX treatment, based on a self-assessment by subjects and an assessment by the treating Investigator. Secondary objectives include an evaluation of the efficacy of ADA + MTX in subjects with Ps and characterization of the possible relationship between serum levels of ADA and efficacy outcomes. The impact of MTX on ADA serum levels will also be assessed by defining the change in serum ADA from baseline following the addition of MTX to therapy. Safety of ADA + MTX will also be assessed.

---

Complete specific details of the statistical analysis will be described and fully documented in the Statistical Analysis Plan (SAP). The SAP will be finalized prior to the database lock.

### **8.1.1 Analysis Population**

The intent-to-treat (ITT) population will be used in the assessment of treatment satisfaction and in the evaluations of ADA + MTX efficacy. The ITT population is defined as:

- All subjects who received at least one dose of ADA and one dose of MTX.

A per protocol population will not be defined for this qualitative study.

The safety population is defined as all subjects who received at least one dose of ADA and one dose of MTX and will be used to evaluate safety of ADA + MTX.

### **8.1.2 Planned Methods for Statistical Analysis**

Point estimates and 95% confidence intervals (CIs) will be provided for the discrete efficacy variables such as the proportion of responders to ADA + MTX. Changes from baseline (in PASI, PGA, DLQI and ADA serum levels) will be estimated using an appropriate estimation from a Mixed Model and statistical tests of change from baseline equal to zero will be carried out at the 0.05 significance level. Descriptive statistics will be provided as appropriate. These include the number of observations, mean, and standard deviation for continuous variables and counts and percentages for discrete variables. The analysis will be performed using SAS® (SAS Institute Inc., Cary, NC, USA).

### **8.1.3 Demographics and Baseline Characteristics**

Demographic and Baseline characteristics of the study subjects will be summarized using descriptive statistics. Characteristics will be defined for the ITT population and for subjects differentiated on the basis of whether they are primary sub-optimal responders or secondary sub-optimal responders at Baseline.

### **8.1.4 Statistical Analysis of Efficacy**

The primary and secondary efficacy analyses will be conducted on the ITT population. The primary efficacy analyses will also be conducted for the following sub-populations:

- Subjects defined as primary sub-optimal responders at baseline, based on Investigator assessment;
- Subjects defined as secondary sub-optimal responders at baseline, based on Investigator assessment.

For the primary and secondary efficacy analyses, sub-optimal responder imputation (imputing missing satisfaction data as “dissatisfied”) will be used. In the event that greater than 5% of the satisfaction data are missing, the following will be carried out to impute the missing data in sensitivity analyses:

- Last observation carried forward (LOCF): The LOCF analyses will use the completed evaluation from the previous visit within the particular period for efficacy measures assessed, to impute missing data at later visits;

Additional exploratory efficacy outcomes will be analyzed using available data at each assessment point and changes over time for PASI, PGA and DLQI scores will be estimated using a Mixed Model. Exploratory analysis to determine associations between ADA serum levels and PASI, PGA and DLQI scores will also be carried out. This could be accomplished using a regression analysis with ADA serum level and visit as explanatory variables and either PASI, PGA or DLQI as response variables and controlling for within subject measurements. To determine the form of the regression model, the exploratory analyses could be carried out using LOESS Regression or general additive models. Alternatively, subjects could be grouped according to predetermined ranges of PASI, PGA or DLQI and the analysis could concentrate on determining differences in ADA serum levels in these groups.

---

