Antibodies against ADA have been shown to contribute to lower treatment response in RA, PsA, CD and AS ([8](#), [14-20](#)). However, information on the relationship between TNF inhibitor serum levels, antibodies and clinical response with respect to Ps is limited ([8,14,15](#)). It is clear that subjects with Ps can develop antibodies against ADA, although the actual reported proportions with an immune response is variable, ranging from 6% following treatment discontinuation and relapse ([21](#)), 8.8% in the pivotal Phase III REVEAL clinical trial ([1](#)) and 16% and 45% in two prospective observational studies ([14,22,23](#)). The latter studies showed that trough levels of ADA were positively associated with clinical response and were significantly lower in subjects with anti-ADA antibodies ([14,22,23](#)). For example, Lecluse et al. ([22](#)) found that in 29 Ps subjects (mean PASI at baseline, 15.5; disease duration 22 years; mean number of prior systemic therapies, 4.2) who were initiated on ADA, 45% had developed anti-ADA antibodies at 24 weeks. In these subjects, titers of anti-ADA antibodies were associated with low ADA serum levels which in turn correlated with low treatment response ([22](#)). A recent study by Mahil et al. ([14](#)) confirms that antibodies against ADA contribute to a poor treatment response in Ps; after 4 weeks, ADA serum levels were significantly higher in clinical responders compared to non-responders ( $p=0.003$ ) and anti-ADA antibodies were detected in 25% of non-responders compared to none of the responders ([14](#)).

In addition to treatment failure, the presence of anti-TNF antagonist antibodies can lead to an increased risk of AEs such as acute or delayed infusion reactions which can decrease adherence to treatment regimens and lower treatment response ([15](#)).

Clinical responses to treatment failure in inflammatory diseases include dose escalation, concomitant administration of an immunosuppressant, or a switch to a different TNF antagonist ([24-27](#)). With ADA, dose escalation is accomplished by decreasing the dosing interval from two weeks to one week, and with respect to Ps, Leonardi et al. ([24](#)) found that 26.6% of subjects who initially failed ADA therapy (defined as subjects with a < PASI 50 response after 24 weeks) were PASI 75 responders 12 weeks after dose escalation. However, dose escalation is associated with increased treatment costs ([24](#)) and

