### **4.2 Secondary objectives**

- To determine the proportion of primary and secondary sub-optimal responders to ADA monotherapy (sub-optimal responders defined as subjects with an unsatisfactory response to treatment based on Investigator assessment) with a PGA  $\geq 3$  and a PASI  $\geq 5$  who reach PASI 50, PASI 75 and PASI 90 16 weeks after initiation of ADA/MTX combination therapy;
- To define the demographic and clinical profile of subjects benefiting from ADA/MTX combination therapy;
- To determine the magnitude, timing and maintenance of the benefit of adding MTX to ADA by assessing Investigator/subject satisfaction with treatment, PGA, PASI

---

 Note that subjects may also be receiving topical treatments if they were prescribed prior to enrolment in this study

 Investigator assessment based on a questionnaire response; see Satisfaction questionnaire section

and Dermatology Life Quality Index (DLQI) at 8, 16 and 24 weeks after addition of MTX to therapy;

- To determine change in DLQI from baseline in subjects initiated on ADA/MTX treatment;
  - To determine change in serum levels of ADA following addition of MTX and to characterize a possible correlation with changes in Investigator/subject satisfaction with treatment, PGA, PASI and DLQI over the study period. Serum levels will be evaluated at baseline (initiation of ADA+MTX) and at weeks 8, 16 and 24.

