### 8.3 Statistical Analysis of ADA Serum Levels

ADA serum concentrations will be summarized at each time point using descriptive statistics including number of subjects, number of non-missing observations, mean, median, standard deviation, coefficient of variation (CV), minimum and maximum as appropriate. Mean and median concentration versus time plots will be generated. Data will be assessed for the following subgroups:

- Total recruited subjects;
- Subjects defined as primary sub-optimal responders at baseline, based on Investigator assessment;
- Subjects defined as secondary sub-optimal responders at baseline, based on Investigator assessment

To further characterize the relationship between ADA serum levels and treatment response, subjects will be classified as non-responders (< 50% improvement in PASI from baseline (baseline defined as addition of MTX to ADA therapy); moderate responders ( $\geq$  50% to <75% improvement in PASI from baseline) or good responders ( $\geq$  75%

---

improvement in PASI from baseline) at 8, 16 and 24 weeks. At each visit, median ADA serum levels will be evaluated by group and compared between groups.

In addition, exploratory analysis to determine possible associations between MTX dose and ADA serum levels will be carried out.

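### The stated adalimumab-response analyses use drug level rather than change in level, and none names satisfaction, so they do not match the secondary objective

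*Protocol*

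**What the plan says.** Protocol section 4.2 sets a secondary objective in two parts: "To determine change in serum levels of ADA following addition of MTX", and then to "characterize a possible correlation with changes in Investigator/subject satisfaction with treatment, PGA, PASI and DLQI over the study period". The protocol synopsis and SAP section 4.1 carry the same objective.

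The methods are in three places.

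- **Protocol section 8.1.4** plans the association analysis: "Exploratory analysis to determine associations between ADA serum levels and PASI, PGA and DLQI scores will also be carried out". It suggests a "regression analysis with ADA serum level and visit as explanatory variables and either PASI, PGA or DLQI as response variables", "controlling for within subject measurements". As an alternative, "subjects could be grouped according to predetermined ranges of PASI, PGA or DLQI" and ADA levels compared across those groups. Both options are put conditionally, so neither is a commitment.
- **Protocol section 8.3** classifies subjects by percentage PASI improvement since MTX was added (below 50%, 50% to below 75%, 75% or more). At each visit "median ADA serum levels will be evaluated by group and compared between groups".
- **Protocol sections 8.1 and 8.1.2** provide for the change in ADA from baseline to be estimated with a mixed model and tested against zero.

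SAP section 3.0 leaves pharmacokinetics to separate documents, which are not among those supplied. SAP section 10.2.2 lists no ADA variable.

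**The concern.** The objective concerns change on both sides: did the subjects whose ADA rose after MTX was added also improve? The stated association analyses put ADA level on one side. Satisfaction, which is the primary endpoint and the first outcome the objective names, appears in none of them.

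This matters because of the protocol's own background. The introduction reports, from earlier studies of ADA-treated psoriasis, that "trough levels of ADA were positively associated with clinical response". If such a link exists between subjects before MTX is added, an analysis of levels can detect it whether or not MTX altered anyone's level. The introduction also gives the mechanism of interest: antibodies lower ADA concentration, and MTX may reduce antibodies. A significant slope from a levels analysis could then be taken as support for that mechanism when it only restates a pre-existing difference between people.

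**Working it through.** **1. Objective against method**

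| Source (protocol) | ADA quantity | Outcome quantity | Satisfaction named? |
|---|---|---|---|
| Objective, 4.2 | change | change in satisfaction, PGA, PASI, DLQI | yes |
| 8.1.4, regression | level | score level (PASI, PGA or DLQI) | no |
| 8.1.4, grouping | level | range of score | no |
| 8.3 | level | PASI improvement group (a change) | no |
| 8.1 and 8.1.2 | mean change, alone | none | no |

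No row below the first pairs change in ADA with change in an outcome.

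**2. The plan's own figures.** The documents give no calculation for this analysis. Their only design figure is the precision of the responder proportion, which reproduces: 1.96 × √(0.5 × 0.5 / 50) = 13.86%, against 13.9% in protocol Table 5. It is used here only for n = 50. The four ADA sampling times (baseline, Weeks 8, 16 and 24) come from section 4.2.

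**3. Why the choice of model decides the matter.** A random-intercept slope is a weighted average:

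slope = w × (between-subject slope) + (1 − w) × (within-subject slope), with w = θB / (W + θB).

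Per subject with T visits and unit ADA variance, W = (T − 1)(1 − ICC of ADA), B = T × (ICC of ADA) + (1 − ICC of ADA), and approximately θ = (1 − ICC of PASI) / [(1 − ICC of PASI) + T × (ICC of PASI)].

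Take T = 4 and PASI ICC 0.8, so θ = 0.2 / 3.4 = 0.059.

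- ADA ICC 0.5: W = 1.5, B = 2.5, θB = 0.147, w = 0.147 / 1.647 = 0.09.
- ADA ICC 0.9: W = 0.3, B = 3.7, θB = 0.218, w = 0.218 / 0.518 = 0.42.

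The steadier a subject's ADA, the more the slope reflects differences between people. With subject fixed effects, w = 0.

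**4. Simulation, first set of assumptions.** n = 50, four visits, 1,000 runs per row, two-sided 0.05. There is no mean change in ADA or PASI, within-subject fluctuations are independent, and the only link is a stable negative correlation between a person's usual ADA and usual PASI. Correlations and ICCs are assumed. Entries are the percentage of trials with a significant ADA-PASI result. Grouping is Week 16 ADA across thirds of Week 16 PASI (Kruskal-Wallis). Change on change is baseline to Week 16 (Pearson).

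| Stable correlation (size) | ICC of ADA / PASI | Random intercept | Grouping by score | Subject fixed effects | Change on change |
|---|---|---|---|---|---|
| 0 | 0.5 / 0.5 | 4.7 | 4.9 | 5.5 | 4.7 |
| 0 | 0.7 / 0.7 | 4.3 | 3.9 | 4.5 | 5.5 |
| 0 | 0.9 / 0.8 | 7.0 | 4.5 | 5.7 | 5.0 |
| 0.3 | 0.5 / 0.5 | 15.3 | 12.1 | 5.1 | 5.4 |
| 0.3 | 0.7 / 0.7 | 17.2 | 17.6 | 5.2 | 5.4 |
| 0.3 | 0.9 / 0.8 | 27.2 | 23.5 | 4.9 | 5.0 |
| 0.5 | 0.5 / 0.5 | 31.9 | 27.2 | 4.5 | 4.5 |
| 0.5 | 0.7 / 0.7 | 39.4 | 44.8 | 5.5 | 5.1 |
| 0.5 | 0.9 / 0.8 | 67.6 | 65.6 | 5.0 | 4.5 |

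**5. Simulation, second set of assumptions.** Between-subject ADA SD 3, stable PASI SD 4 and residual SD 2 (PASI ICC 16 / 20 = 0.80), with PASI falling independently of ADA. With within-subject ADA SD from 1.5 to 0.5 (ADA ICC 9 / 11.25 = 0.80 to 9 / 9.25 = 0.97), the random-intercept slope is significant in 18% to 46% of trials at correlation 0.3 and 41% to 88% at 0.5. With within-subject SD 3 (ICC 9 / 18 = 0.50) this falls to 9% to 18%. Fixed effects and change on change stay at about 5%.

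**6. Section 8.3.** Assumed mean improvement 50%, residual SD 30 points, ADA ICC 0.8, 2,000 runs. If improvement is unrelated to a subject's stable ADA, the level comparison is significant in 5.2% of trials. If improvement depends on stable ADA by 10, 15 or 20 points per SD, it is significant in 29%, 59% or 80%, although ADA did not change. Comparing change in ADA between the same groups gives about 4% throughout.

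**The case against.** Several points stand against a stronger reading.

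- **A reader might infer that the planned model will produce a spurious signal.** The documents do not support that. The regression is optional, and its phrase "controlling for within subject measurements" fits subject fixed effects as well as a random intercept. Under fixed effects the problem disappears.
- **A reader might infer that the whole plan relates level to level.** Section 8.3 groups by PASI improvement, which is a change. It keeps its nominal error rate unless improvement itself depends on stable ADA.
- **A reader might infer that a failure of MTX to move ADA would go unseen.** Sections 8.1 and 8.1.2 test mean change in ADA, so that result would be reported alongside. It shows whether ADA moved on average, not whether those who moved were those who improved.
- **A reader might infer that the link with satisfaction is never examined.** The synopsis and section 8.1 promise to characterise the relationship of ADA with efficacy outcomes generally, and the unseen pharmacokinetic documents may cover it. What can be said is that no stated method names it.
- **The percentages are not false-positive rates for the question section 8.1.4 poses.** If a stable association exists, detecting it is correct. The error would lie in attributing it to change after MTX, which section 8.1.4 does not do.

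The size of any stable association is also assumed. The introduction supports its direction, but in other cohorts. This trial enrols only sub-optimal responders with PGA of at least 3 and PASI of at least 5, in whom it may be weaker.

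These points limit the concern. They do not supply the missing analysis of change against change.

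**Conclusion.** The mismatch holds on the text alone: no stated method links a subject's change in ADA to change in any outcome, and none names satisfaction. This rests on no assumption beyond the absence of the separate pharmacokinetic documents.

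The consequence is conditional. With a random intercept, or with grouping by score range, a stable between-subject association can give a significant result though ADA only fluctuated at random. For assumed correlations of 0.3 to 0.5, the random-intercept model does so in roughly 10% to 90% of trials (9% to 88% across the settings), depending mainly on how steady ADA is within a subject. Change on change gives about 5%. The 0.05 level is itself an assumption, because the protocol states it for tests of change from baseline and not for these associations.

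The analysis is exploratory. It serves a stated secondary objective and does not affect the primary endpoint. A modest correction is warranted.

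**What to change.** In protocol sections 8.1.4 and 8.3, and in the pharmacokinetic analysis document:

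1. Make the analysis for this objective change from baseline in ADA against change in PASI, PGA and DLQI. Alternatively, fit a repeated-measures model with subject-mean ADA and the deviation from it as separate terms, or with subject fixed effects. Name the method chosen.
2. Compare change in ADA between subjects with and without satisfactory response at Week 16, once by Investigator and once by subject rating. Protocol Table 1 schedules the questionnaires at screening and not at the Baseline visit, so any change in satisfaction runs from screening. Eligibility requires Investigator dissatisfaction at screening, so a satisfactory Investigator rating at Week 16 is already a change.
3. Keep the level-based comparisons as descriptive.
4. Describe the within-subject result as association after MTX was added, not as an effect of MTX. Section 5.6.1 confirms that there is no control group, and within-subject variation also includes missed doses and natural fluctuation.

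The cost is wording only, because all the data are already collected. The downside is that the within-subject estimate is less precise than the pooled slope.

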**8.1.5 Statistical Analysis of Safety**

All AEs, SAEs, and AEs leading to discontinuation will be collected during the study and up to 70 days after the last dose of ADA. Safety analyses will be carried out using the Safety Population. A treatment-emergent AE is defined as an event with onset or worsening after the first dose of study drugs (ADA + MTX) and within 70 days after the last dose of ADA. The number and percent of subjects experiencing treatment-emergent AEs will be tabulated using the Medical Dictionary for Drug Regulatory Activities (MedDRA®) system organ class and preferred term. Summaries (including percentages and event per 100 patient-years) of SAEs, deaths and AEs leading to discontinuation from the study will be provided as well.

